5.0 Participant Selection

Approximately 400 adult hepatology patients with poor prognosis (identified by the ‘surprise question’ see below) will be randomized to receive either usual hepatic care (control group, N=200) or usual hepatic care with comprehensive palliative care services (intervention group, N=200). Any Vanderbilt patient admitted to the primary inpatient service of one of the study hepatologists with limited life expectancy may be eligible for participation. We expect a participation rate of ~75% (based on the participation rate of a similar study conducted by [name]), and no more than 10% of patients excluded based on eligibility criteria. We are powered to detect a 13% difference in readmission rate between treatment arms with 400 participants, assuming equal mortality across arms (see section 8.0, Statistical Analyses). As this is an internally funded study, we will have flexibility to enroll patients past the the accrual goal of 24-months in order to enroll 400 participants if necessary.

Inclusion Criteria:

- Inpatient at Vanderbilt University Medical Center with advanced liver disease, whose treating hepatologist indicates a ‘No’ response to the question, “Would you be surprised if this patient died within 1 year?”

Exclusion Criteria:

- Age < 18 years
- Inability to give written informed consent (patient or surrogate decision-maker)
- Inability to respond to questions in English
- Treating hepatologist denies permission to enroll
- Receiving hepatology care at non-Vanderbilt sites (to ensure appropriate follow-up)

Recruitment

Potential patients will be identified within StarPanel using hepatology service codes and/or attending physician name. Patients’ electronic medical records will be manually reviewed by study personnel to confirm preliminary eligibility. Once preliminary eligibility is established, the treating hepatologist will receive a prompt via email with a REDCap survey link to respond to the question, “Would you be surprised if this patient died within 1 year?” The ‘surprise question’ has been used in a variety of patient populations for prognosis and to evaluate appropriateness for palliative care^{25,26} and has shown specificity (69.3%) and

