If the patient does not have the capacity to give written informed consent due to his/her current health state, the surrogate will provide written informed consent prior to the patient's enrollment in the study. The patient will be re-evaluated periodically for the capacity to give consent. The SC will confirm with the treating hepatologist if the patient is capable of providing written informed consent while inpatient. If the patient is found capable, the study coordinator will obtain written informed consent from the patient. If the patient is found to be capable, but is discharged prior to providing written informed consent, the study coordinator will contact the patient by telephone. The patient will sign the e-consent form in a similar manner as the surrogate decision-maker e-consent procedures described above. If the patient does not have access to a computer, and the patient provides verbal permission, a paper informed consent form for the patient to sign and return, a blank copy for the patient to keep, and a stamped addressed envelope to return the signed copy will be mailed to the patient. If the patient is found capable and declines participation, the patient and surrogate will be immediately terminated from the study. Study staff will print a copy of the signed document, and give to participant at time of study visit. Should a participant choose to receive a link to the consent document in lieu of a hard copy (or if they sign electronically from a remote location), they will receive a link to a ROCKET site containing the consent form appropriate to the version date that they signed. Signed consent documents will NOT be housed electronically on ROCKET. No research procedures will be performed until after consent has been provided.

After written informed consent is provided by the patient or surrogate, baseline measures will be completed, and patients will then be randomized (stratified by treating hepatologist) to the control or intervention arm using validated computer programs (**see Figure 3**). If the surrogate decision-maker provided consent for

the patient, patients will be randomized, but baseline measures will be completed by the patient after providing written informed consent. A panel within the EMR containing all enrolled patients and the arm assignment will be created and shared with the PC team.

[figure not shown]

Figure 3. Approach for Study Participant Selection

Caregiver Participation

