8.0 Statistical Analyses

Power Calculations

Power calculation was conducted on the primary outcome (time to first hospital readmission) using Cox proportional hazards model accounting for competing risk of death.³⁹ Assuming 50% 1-year mortality in both arms of the expected study cohort (‘surprise question’ inclusion which is comparable to a 50% 1-year mortality rate), with type I error of 0.05 and power of 80%, the minimum detectable hazard ratio (HR) under sample size N=400 was calculated given varying hospital readmission rate in the usual care arm ranging from 0.5 to 0.9. The corresponding rate reduction in the intervention arm (DR) and the relative rate reduction (RDR) were also provided. See **Table 3**. To assess clinical rationale of the power calculation, 1-year hospital readmission rate was assessed from pilot data obtained from a retrospective data pull via the Research Derivative. Admission to a study hepatologist during a 3-month window was required for cohort inclusion, and subsequent admission data (1-year post ‘qualifying admission’) was analyzed. Of the 151 patients included in the pilot data, 93 patients (62%) were readmitted within 1 year of the qualifying admission with a 1-year mortality rate of 35%. This pilot cohort (35% mortality rate) may be healthier than expected study cohort. However, due to competing risk of death, we are not sure whether the 1-year readmission rate of 62% from the pilot cohort is an overestimate or underestimate of the target population. Nonetheless, the proposed sample size provides sufficient power (80%) to detect rate reduction

of 13% when the hospital readmission rate in the usual care arm is between 50% and 70%, which is comparable with the pilot data.

Table 3

Various risk of readmission in the usual care arm (R), and the corresponding minimum detectable hazard ratio (HR) and the corresponding inverse HR (1/HR), difference of risk of readmission (DR) and relative difference of the first readmission (RDR) under sample sizes N = 400 with power 80% and type I error 0.05.

N = 400				
R	HR	1/HR	DR	RDR
50%	0.67	1.5	13%	0.26
60%	0.69	1.4	13%	0.22
70%	0.71	1.4	13%	0.18
80%	0.73	1.4	11%	0.14
90%	0.74	1.4	8.3%	0.092

Analyses Plan

Demographic and clinical characteristics of the participants such as age, gender, etc. will be compared between the control and the intervention arms using Wilcoxon rank-sum test for continuous variables and Pearson's Chi-square for categorical variables.

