Aim 1: Time to first hospital readmission within 1-year post randomization will be compared across treatment assignment using Cox proportional hazards model, accounting for the competing risk of death and adjusting for relevant demographic and clinical characteristics. A less than 1 hazard ratio for the treatment group status implies reduced readmission rates in the intervention arm given equal mortality rates.

Aim 2: Days alive out of hospital within 6-months post randomization, total days in hospital and ICU within 1-year post randomization, number and cost of hospital admissions within 1-year post randomization, median length of stay per admission, number of transfers to hospice within 1-year post randomization, time to hospice placement after referral, survival, presence of advance directives within 1-year post randomization, presence of physical symptoms, transplant status listing (deferred, listed, declined), and number of completed liver transplants will be obtained via chart review and compared across treatment assignment using proportional odds model for ordinal outcomes, Cox proportional hazards model for time-to-event outcome and logistic regression for binary outcomes, adjusting for relevant demographic and clinical characteristics.

Aims 3 and 4: Both cross-sectional and longitudinal analysis will be conducted to compare between group differences in CLDQ. For the cross-sectional study, for each time point of data collection, linear regression with ordinary least square will be used with CLDQ as the dependent variable (DV) and treatment assignment (0 for control arm and 1 for the intervention arm) as the independent variable (IV) of interest adjusting for baseline CLDQ and potential confounding factors based on clinical and statistical considerations. A positive value of the regression parameter for treatment status indicates higher CLDQ in the intervention arm. For longitudinal analysis, linear mixed model will be adopted including follow-up time and the interaction between follow-up time and treatment group on top of the cross-sectional model. The interaction term is included to compare decreasing rate of CLDQ between groups with a positive value of the corresponding regression parameter indicating slower decline rate of CLDQ in the intervention arm.

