The same series of analyses for the CLDQ will be conducted for the PROMIS (depression, anxiety), ED-5D-5L, the Quality of End-of-Life Care patient and caregiver questionnaires, and the KCSS. Histogram of baseline secondary outcomes will be used to evaluate ceiling/flooring effect and degree of skewedness. Appropriate transformation such as log transformation will be considered for highly skewed secondary outcomes to improve efficiency. A positive value of the main effect for intervention status in the cross-sectional analyses and a positive value of the interaction effect in the longitudinal analyses indicate favorable intervention effect.

Aim 5: Summary descriptive measures such as mean, quartiles and standard deviation for continuous variables and frequencies for categorical variables will be provided for process outcomes from participants in the intervention arm to evaluate fidelity of the proposed intervention and generalizability of implementing a large-scale intervention program. The following data will be collected for each arm: percentage of patients with answered surprise question (stratified by provider), percentage of patients with a 'No' response to the surprise question (stratified by provider), percentage of patients with 'No' response to the surprise question who were approved for study enrollment (stratified by provider), percentage of intervention patients who received initial PC inpatient consult, percentage of patients who received scheduled follow-up telephone contact, percentage of patients who attended an appointment for care after referral was obtained, percentage of patients with completed questionnaires at each time point, percentage of patients who received Palliative Care materials, and percentage of patients who received an inpatient PC consultation upon hospital readmission during the intervention phase will be calculated.

Interim Analysis

Interim analysis will be conducted when N=30 and N=150 participants are enrolled and followed for at least 6 months to evaluate whether the study is feasible, study procedures are conducted as intended, and that there is not significant patient dropout for mortality or other reasons.

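### Randomisation is stratified by treating hepatologist, but no model for Aims 1 to 4 commits to including the hepatologist

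*Combined protocol and SAP*

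**What the plan says.** Section 5.0 (Consent Procedures) states that "patients will then be randomized (stratified by treating hepatologist) to the control or intervention arm". No other stratification factor is named.

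The Analyses Plan in section 8.0 treats covariates as follows.

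- **Aim 1 (primary, time to first readmission):** a Cox model "accounting for the competing risk of death and adjusting for relevant demographic and clinical characteristics".
- **Aim 2 (utilisation, survival and other chart outcomes):** proportional odds, Cox and logistic models with the same general covariate wording.
- **Aims 3 and 4 (CLDQ):** linear regression at each time point, adjusted for baseline CLDQ and "potential confounding factors based on clinical and statistical considerations". The mixed model adds only follow-up time and its interaction with treatment. The other questionnaires use the same models.
- **Aim 5:** provider appears here alone, as a breakdown of descriptive screening percentages.

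No effect model names the hepatologist as covariate, stratum, random effect or cluster.

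**The concern.** When randomisation is balanced within a factor that predicts outcome, the arm comparison varies less than an analysis ignoring that factor assumes. The standard error is then too large and the test conservative. In a Cox model, leaving out a factor that affects the hazard also pulls the hazard ratio towards 1, so power falls.

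There is reason to think the factor could matter. The treating hepatologist answers the surprise question that defines eligibility, and one exclusion criterion reads "Treating hepatologist denies permission to enroll". Case mix may therefore differ between hepatologists, although the documents do not say by how much.

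The second issue is the open choice. An analyst could decide after seeing outcomes whether hepatologist counts as a relevant characteristic, and picking the more favourable test inflates type I error.

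**Working it through.** **1. The plan's own figure.** Table 3 gives minimum detectable hazard ratios of 0.67, 0.69, 0.71, 0.73 and 0.74 for usual-care readmission R of 50% to 90% at N = 400. Freedman's formula, with two-sided alpha 0.05, 80% power and 400 × R events, is HR = (s − 1)/(s + 1), where s = √(400R/K) and K = (1.96 + 0.842)² = 7.85. At R = 60%, s = √(240/7.85) = 5.53 and HR = 4.53/6.53 = 0.69. The five rows give 0.669, 0.694, 0.713, 0.729 and 0.743, which all match. No hepatologist term enters, so the point does not depend on an error in Table 3.

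**2. Simulation setting for Aim 1.**

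- From section 8.0: N = 400 in equal arms, R = 60%, HR 0.69, 50% one-year mortality.
- Death hazard: −ln(0.5) = 0.693. A control readmission hazard of 1.463 gives cumulative readmission 1.463/2.156 × (1 − e^−2.156) = 60%.
- Intervention hazard: 1.463 × 0.69 = 1.009, giving 1.009/1.702 × (1 − e^−1.702) = 48.5%.
- Readmissions: 200 × (0.600 + 0.485) = 217.
- Power with no hepatologist effect (Schoenfeld): Φ(√(217/4) × 0.371 − 1.96) = Φ(0.77) = 78%. This is below 80% because Table 3 applies R to both arms.
- Assumed, not in the documents: number of hepatologists, permuted blocks of 4, and a normal hepatologist effect on the log hazard. SD means the spread left after covariate adjustment.
- Death is treated as censoring and follow-up ends at one year. There were 40,000 trials per cell at SD 0 and 0.2, and 20,000 at SD 0.4 and 0.6.

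**3. Change in power from stratifying the log-rank test (percentage points).**

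| Hepatologists | SD 0 | SD 0.2 | SD 0.4 | SD 0.6 |
|---|---|---|---|---|
| 6 | −0.6 | +0.2 | +3.4 | +8.3 |
| 8 | −0.9 | 0.0 | +3.1 | +7.6 |
| 12 | −1.4 | −0.5 | +2.5 | +7.5 |
| 20, equal | −2.8 | −1.6 | +1.4 | +6.4 |
| 20, uneven, those under 10 patients pooled | −1.5 | −0.7 | +2.0 | +6.5 |
| 40, ten patients each | −6.1 | −5.4 | −2.1 | +2.9 |

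With 8 hepatologists at SD 0.4, power goes from 73.3% to 76.4%. Repeat runs of 5,000 and 12,000 trials per cell gave +2.5 to +3.2 at SD 0.4 and about +8 at SD 0.6. Two variations with 8 hepatologists change little: unequal volumes give −1.0 / −0.3 / +2.7 / +7.1, and keeping deaths in the risk set to one year (subdistribution type) gives −0.2 / +0.6 / +2.7 / +7.1.

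**4. What these SDs mean.** One-year readmission for hepatologists one SD below and one SD above average is 54% and 66% at SD 0.2, 48% and 72% at SD 0.4, and 42% and 77% at SD 0.6.

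**5. Type I error.** With 8 hepatologists, the unstratified test rejects in 4.3% of null trials at SD 0.4 and 3.6% at SD 0.6. The stratified test stays at 4.7% to 5.2% throughout. Taking whichever test is significant gives 5.9% to 6.1% with 6 to 12 hepatologists, against 5.1% to 5.2% for either alone.

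**6. Linear models, Aims 3 and 4.** With 8 equal strata, the reported standard error exceeds the true one by roughly √[(1 − ICC/8)/(1 − ICC)]. For assumed residual ICCs of 0.02, 0.05 and 0.10 that is 0.9%, 2.3% and 4.8%. Simulation gave 0.5%, 2.2% and 4.5% (Monte Carlo error about 0.35%), and 0.3%, 1.4% and 2.0% if half the patients are lost to death. The estimate is unbiased. The size for the Aim 2 models was not calculated.

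**The case against.** The strongest reply is that the plan does not exclude the hepatologist. A randomisation stratum is a natural statistical consideration, so the Aims 3 and 4 wording in particular could cover it. That is true of permission but not of commitment, and a treating physician is not plainly a patient's demographic or clinical characteristic, which is the Aims 1 and 2 wording.

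Second, the omission harms no validity property: there is no type I inflation from a fixed unstratified analysis and no bias in the linear models. This stands. The inflation to about 6% arises only if someone chooses between tests after seeing results; nothing in the documents says that is planned, and it is partly a consequence of the open covariate list in general.

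Third, the benefit rests on assumed inputs. At SD 0.2 or less, stratifying is neutral or slightly harmful with 6 to 20 hepatologists, and the gains of 6 points or more need a spread of about 42% versus 77% within one hospital's service after adjustment. No passage supports a spread that large. This also stands, and it limits the weight of the point. Section 4.0 was not in the text reviewed and may state how many hepatologists take part, so the missing count is not held against the plan.

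Finally, stratifying makes the Aim 1 hazard ratio a within-hepatologist ratio. That is a different estimand, not a bias correction, and should be described as such.

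**Conclusion.** The gap is real but modest: the analysis does not commit to the one factor on which the randomisation is built. It matters mainly for the primary Cox model, where the cost is lost power if hepatologists differ.

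Under the assumed setting, the residual SD at which stratifying breaks even is about 0.15 to 0.25 with 6 to 12 hepatologists, 0.33 with 20 and 0.5 with 40. Above that the plan gives up power, around 3 points at SD 0.4 and 8 at SD 0.6 for 6 to 12 hepatologists. Below it, stratifying costs a little. The true number of strata, block size and spread are unknown, so these figures show scale and do not predict this trial. For the questionnaires the effect is small. The point is worth considering because the change is cheap and removes a choice that would otherwise be open after unblinding.

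**What to change.** Add to section 8.0:

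- The Aim 1 model and the other Cox or competing-risk models are stratified by treating hepatologist at randomisation.
- Hepatologist is included in the logistic, proportional odds, linear and mixed models, as a random effect if there are many small strata.
- Hepatologists with very few patients are pooled by a rule set without reference to trial outcomes. With many small strata this rule is essential, because stratifying without it can itself lose power.
- Hepatologist indicators are not entered as Cox covariates when strata are sparse. At SD 0, the Wald test for treatment then had type I error of 5.3% with 8 hepatologists, 5.6% with 12, 5.9% with 20 and 7.6% with 40.

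To set the rule, the sponsor can use the pilot data, since "Admission to a study hepatologist during a 3-month window was required for cohort inclusion". They can supply the number of hepatologists, their volumes and a rough spread. The spread will be imprecise: 93 readmissions over, say, 8 hepatologists gives a log-hazard standard error of about √(8/93) = 0.29 each, and section 8.0 says this cohort may be healthier than the trial population.

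The cost is a short SAP addition and no new data. If hepatologists turn out not to differ, the price is 0.6 to 1.4 points of power with 6 to 12 hepatologists, 2.8 with 20 equal strata (1.5 with uneven strata and pooling under 10), and 6.1 with 40 strata of ten left unpooled.

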2.0 Rationale and Specific Aims

We will conduct a randomized, controlled study to evaluate the effectiveness of a systematic comprehensive palliative care intervention on patient outcomes in hepatology patients with poor prognosis. Our specific aims are to:

- 1) **Assess the impact of systematic, comprehensive palliative care services compared to usual hepatic care on time to first hospital readmission within 1-year post randomization.**
- 2) **Assess the impact of systematic, comprehensive palliative care services compared to usual hepatic care on other hospital utilization variables (including days alive out of hospital within 6-months post randomization, total days in hospital and ICU within 1-year post randomization, number and cost of hospital admissions within 1-year post randomization, median length of stay per admission, number of transfers to hospice within 1-year post randomization, time to hospice placement, and survival).**
- 3) **Assess the impact of systematic, comprehensive palliative care services compared to usual hepatic care on quality of life.**
- 4) **Assess the impact of systematic, comprehensive palliative care services compared to usual hepatic care on patient satisfaction and caregiver stress and satisfaction.**
- 5) **Evaluate the fidelity of the palliative care intervention and assess the generalizability of implementing a large-scale Palliative Care program.**

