6.0 Intervention

We will conduct a randomized, controlled study to evaluate the impact of systematic, comprehensive palliative care services vs. usual hepatic care. After providing written informed consent, patients will complete baseline measures including demographic (**Appendix C**), mood, and quality of life questionnaires on the inpatient unit. Patients will be randomized to either the control (usual hepatic care) or the intervention arm (usual hepatic care with comprehensive palliative care services). Patients who are randomly assigned to usual care will not be scheduled to meet with the palliative care service unless a meeting is requested by the patient, the family, or the treating physician.

Patients randomized to the intervention arm will receive a binder (**Appendix D**) of patient materials including general information about palliative care services, the COMPASS study, and templates to document information if the patient wishes (names of medicine, upcoming appointments, important contact information, etc.). Intervention patients will also receive , contact information printed on a magnet (**Appendix F**), a wallet card (**Appendix G**), and a one-page handout (**Appendix H**). A VUMC palliative care physician or nurse practitioner will meet with the patient and appropriate surrogate, caregiver, family members, etc. after randomization to provide a verbal overview detailing palliative care services and to provide the comprehensive initial consult. Appropriate palliative care providers will provide follow-up in-person consults while the patient remains inpatient per usual palliative care services.

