During the telephone contact, if a palliative care nurse identifies a need for further care (e.g., referral to hospice, appointment with the outpatient palliative care office, appointment for symptom management, etc.), the nurse will engage the palliative care team and/or the Hepatology team as indicated. Nurses will relay all relevant information from the telephone contacts to the palliative care team and the treating hepatologists via StarPanel and other clinically appropriate communication channels. If the patient is readmitted to the hospital, the inpatient in-person follow-up and outpatient telephone follow-up schedule will restart. Patients will receive inpatient consultations and follow-up outpatient telephone consultations for one year after randomization to the intervention arm or until death.

After completion of the one-year intervention phase, patient participation will be complete. With the exception of the follow-up telephone contacts and patient-friendly materials, similar services are available to all patients per routine practices. There are no other investigational agents or processes being used for the intervention group of patients/providers. See **Figure 4** below for trial design.

[figure not shown]

Figure 4. RCT Study Schema

The palliative care intervention is expected to include:

- Informational, patient friendly Palliative Care Binder, magnet, handout, wallet card
- Establishment of a palliative care plan
- Care coordination by palliative care team
- Early and regular ongoing engagement of palliative care physicians and nurse practitioners for inpatient consultations
- Telephone contacts conducted by trained palliative care nurses to review palliative care plan, assess changes in symptoms, identify patient needs and re-engage the palliative care team or Hepatology team as appropriate for referrals or appointments
- Communication by palliative care team to all providers and teams involved in patient's care
- Systematic collection of information, including identification of surrogate or health care proxy and advance care planning

Inpatient and telephone palliative care consults will consist of a systematic process utilizing standardized template forms and will include all of the components outlined in **Table 1**.

Table 1

Palliative Care Intervention Procedures	Inpatient In-Person Consults	Outpatient Telephone Consults
Introduction to PC	X	
Introduction to concepts of Advance Directive, living will, healthcare agent	X	

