Assess physical and mental functioning	X	X
Review and complete Advance Directives including: review of previously completed advance care directives, discussion/ completion of POST form, code status, and advance care directives (power of attorney, living will, or advance care plan)	X	X
Name surrogate	X	
Review medical history	X	
Review family history	X	
Review social history (marital status, tobacco use, smoking, alcohol use, drug use, occupation, children) and identify patient's barriers to healthcare access	X	
Dignity and Spirituality assessment (referral to chaplain where applicable)	X	X
Review medications and allergies	X	X
Review symptoms*	X	X
Explain medical condition/diagnosis in lay terms and discuss patient's understanding of prognosis	X	
Discuss questions to ask hepatologist	X	X
Discuss social/family support system	X	X
Develop Care Plan and Goals of Care in the context of the patients current medical condition	X	
Review Care Plan and Goals of Care in the context of the patients current medical condition	X	X
Direct/refer patient towards appropriate resources (e.g. hospice where applicable)	X	X
Record time spent with patient	X	X
Ensure family awareness as applicable	X	X
Communication of Care Plan and pertinent information back to Hepatology MD	X	X

*Symptoms include: lack of energy, lack of appetite, pain, dry mouth, weight loss, drowsiness, shortness of breath, constipation, diarrhea, difficulty sleeping, nausea, vomiting, fever, chills, sweats, sore throat, headaches, change in vision, polyuria, polydipsia, cold/heat intolerance, cough, hemoptysis, chest pain, palpitations, orthopnea, hematuria, renal stones, melena, anorexia, enlarged lymph nodes, bleeding, easy bruising, rhinitis, skin reactions, joint pain/swelling, weakness, myoclonus, sadness, agitation, anxiety, confusion, rash

Outcomes

Primary clinical endpoint:

- Time to first hospital readmission within 1-year post randomization

Secondary outcomes are expected to include:

- Days alive out of hospital within 6-months post randomization
- Total days in hospital within 1-year post randomization
- Total days in ICU within 1-year post randomization
- Number of hospital admissions within 1-year post randomization
- Cost of hospital admissions within 1-year post randomization
- Median length of stay per admission
- Number of transfers to hospice within 1-year post randomization
- Time to hospice
- Liver disease-specific health-related quality of life
- Generic measures of quality of life

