- Patient mood
- Patient satisfaction with care
- Caregiver reported stress
- Caregiver reported satisfaction with patient care (including quality of death and dying, as applicable)
- Liver transplant status (deferred, listed, decline)
- MELD score
- Number of completed liver transplants
- Patient diagnoses and physical symptoms (e.g., presence of ascites, variceal bleeding, encephalopathy, delirium)
- Presence of Advance Directives (Goals of Care, Code Status, Surrogate decision-maker, etc.)
- Survival
- Staff satisfaction with intervention procedures

Process outcomes to measure intervention fidelity are expected to include:

- Number of responses to surprise question, number of 'No' responses to surprise question, number of patients with 'No' response to surprise question who are approved for enrollment
- Number of enrolled patients who receive the palliative care intervention
- Use of standardized forms by palliative care providers
- Clear documentation of a plan of care
- Concordance with goals of care (EMR derived, standardized, objective and measurable variables including DNR order non-adherence, aggressive treatment at end of life without expressed patient consent, CPR, mechanical ventilation, intubation, feeding tubes, re-admission, medications, etc.)
- Documented referrals/coordination with social workers or hospice when applicable
- Documented communication of Palliative Care Plan to patient's hepatology provider
- Completed Advance Directive, including designation of a Surrogate Decision Maker

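### Aim 2 appears to time hospice placement from referral, a step the intervention is meant to change, so the comparison between arms would not be a randomised one

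*Combined protocol and SAP*

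**What the plan says.** The outcome is named in four places.

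- Section 2.0, specific aim 2: "time to hospice placement, and survival", with no time origin.
- Section 6.0, Outcomes: "Time to hospice", with no time origin.
- Section 7.2: referrals to hospice and the time until placement are items for chart review, again with no origin.
- Section 8.0, Analyses Plan, Aim 2: "time to hospice placement after referral, survival, presence of advance directives within 1-year post randomization". Only here is referral attached to the outcome.

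Section 8.0 assigns a Cox model to time-to-event outcomes under Aim 2, compared by treatment assignment with covariate adjustment. For this outcome it states no clock start, no analysis set, and no handling of patients who are never referred or who die first.

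Section 6.0 describes how referral arises. Table 1 lists "Direct/refer patient towards appropriate resources (e.g. hospice where applicable") for both inpatient and telephone consults. The telephone nurse acts when she or he "identifies a need for further care (e.g., referral to hospice") and involves the palliative care or hepatology team. The fidelity measures include "Documented referrals/coordination with social workers or hospice when applicable". Usual-care patients will "not be scheduled to meet with the palliative care service unless a meeting is requested by the patient, the family, or the treating physician", although, apart from the calls and printed materials, "similar services are available to all patients per routine practices".

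**The concern.** Aim 2 asks what palliative care does to hospital and hospice use compared with usual care. A clock that starts at referral can include only referred patients. Referral follows from the intervention in one arm and from routine practice or request in the other, so the two referred groups need not be alike. Adjusting for measured covariates does not restore the randomised comparison. The interval in which the intervention could act most, from randomisation to referral, is not counted.

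The analysis plan also counts transfers to hospice within 1 year, which shows how often hospice is used. On the from-referral reading, no planned outcome shows whether patients reach hospice sooner after randomisation. A hazard ratio reported as a treatment effect would instead describe the speed of placement in two self-selected groups.

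**Working it through.** The documents give no hospice referral rate, lag, event count or power for this outcome, so there is no stated figure to reproduce. The point rests on the text; the numbers only illustrate it.

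**Reading the text.** In the Aim 2 sentence of section 8.0, days alive out of hospital, days in hospital and ICU, admissions and transfers to hospice all carry a post-randomisation window. The hospice-time item carries referral instead. The natural reading is a clock from referral. Section 6.0 places referral among the things the intervention does and by which its fidelity is judged.

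**Inputs.** From the documents: 200 per arm (section 5.0) and 50% 1-year mortality in both arms (section 8.0, Power Calculations). Everything else is assumed. Times are exponential unless stated, follow-up is 1 year, and Cox models compare arms with death censored.

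**1. Who enters, and what each clock measures.** The probability of referral before death within 1 year is

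p = λr/(λr+λd) × [1 − exp(−(λr+λd))], with λd = ln 2 = 0.693.

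- Low end, usual care λr = 0.148: 0.148/0.841 × (1 − e^−0.841) = 0.100, or 20 of 200. Intervention at 1.5 times, λr = 0.222: 0.222/0.915 × (1 − e^−0.915) = 0.145, or 29 of 200. Total 49.
- High end, usual care λr = 0.758: 0.758/1.451 × (1 − e^−1.451) = 0.400, or 80 of 200. Intervention at 2 times, λr = 1.516: 1.516/2.209 × (1 − e^−2.209) = 0.611, or 122 of 200. Total 202.
- Patients left out: 400 − 202 = 198 to 400 − 49 = 351.

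With a mean lag of 7 days in both arms (3,000 simulated trials per setting), the from-referral hazard ratio is 0.99 to 1.00, as equal lags imply. The from-randomisation hazard ratio is 1.5 to 2.0, as the assumed referral ratio implies. The two measures answer different questions; this does not show bias.

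**2. When the from-referral hazard ratio is biased.** Two further assumptions are needed: placement speed depends on severity, and the severity mix of referred patients differs by arm. Take half the patients as severe, 1-year mortality 70% v 30% (average 50%), and a mean lag of 7 days in severe patients. Referral hazards per year, severe / less severe, are 0.606 / 0.100 in usual care and 0.895 / 0.445 with intervention. Then 18% v 34% are referred, and 78% v 55% of those referred are severe. Lag depends on severity only, never on arm.

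| Less severe lag ÷ severe lag | From-referral HR, severe share 78% v 55% | From-referral HR, severe share 78% in both arms |
|---|---|---|
| 0.5 | 1.14 | 1.01 |
| 1 | 1.00 | 1.00 |
| 1.5 | 0.91 | 1.00 |
| 2 | 0.85 | 1.00 |
| 3 | 0.80 | 1.00 |

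The last column is a control run with intervention hazards 0.895 / 0.135. In the main run the from-randomisation hazard ratio is about 2.1. An intervention that brings more patients to hospice and leaves the lag unchanged could thus appear to slow or to speed placement. The direction cannot be predicted from the documents.

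**3. What a from-randomisation clock cannot do.** Suppose the intervention changes only the timing of referral: 40% of patients eligible, mean lag 5 days, referral 14 days before death in usual care v 42 or 74 days with intervention. If patients dying within the lead time are referred on day 0, the hazard ratio is 1.15 or 1.21, with power of 9% or 14%. If those patients are not referred, it is 1.03 or 0.99, with power of 5%.

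**The case against.** The strongest reply is that section 8.0 never says the clock starts at referral or that unreferred patients are excluded. The words could mean placement that follows a referral, timed from randomisation. What is certain is an undefined origin. That is fair, and the selection problem is conditional on the reading. But on the other reading the origin is still unstated in all four places, and the same clarification is needed.

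Second, no distortion follows from the documents alone. This stands. Bias away from 1 needs the assumptions in step 2, and at trial size those inputs give about 200 × 0.18 = 36 v 200 × 0.34 = 68 referred patients. The standard error of the log hazard ratio is then about √(1/36 + 1/68) = 0.21, so the extreme value of 0.80 (log −0.22) lies about one standard error from no effect. The objection to the planned comparison is that it cannot be interpreted as an effect of assignment, whatever the size of the bias.

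Third, the remedy partly overlaps with the count of transfers and has little power for a pure timing effect. Both are true. The count still does not show when patients reach hospice.

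Fourth, referral-to-placement lag is a legitimate process measure. Agreed, and it can be kept as a description.

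A small point also stands: section 5.0 does not exclude patients already referred to hospice at enrolment, so a from-referral clock might also include some referrals made before randomisation.

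**Conclusion.** The concern holds. On the natural reading of section 8.0, the hospice-time comparison is limited to patients selected by an event that the intervention is meant to change, so its hazard ratio does not estimate an effect of assignment and cannot answer Aim 2. Confidence is moderate, because the conclusion depends on that reading. The size is unknown. Under the stated assumptions, 198 to 351 of 400 randomised patients would not enter the comparison, and the from-referral hazard ratio could lie anywhere from 1.14 to 0.80 with no true effect on the lag. It stays at 1.00 to 1.01 if the severity mix is the same in both arms. The damage is confined to one secondary outcome. The primary endpoint and the sample size are untouched.

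**What to change.** In section 8.0, Aim 2, replace the item with time from randomisation to hospice placement within 1 year, analysed in all randomised patients by assigned arm. Treat death without hospice as a competing event, and show cumulative incidence by arm beside the Cox cause-specific hazard ratio. Use the same definition in section 2.0, in the section 6.0 outcome list and in section 7.2. If the referral-to-placement lag is kept, report it descriptively by arm among referred patients and not as a treatment effect.

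The cost is small: changes of wording and analysis code, with no new patient contact. The time to placement planned in section 7.2 already requires a placement date. There are two drawbacks. Hospice entry from home may be incompletely captured by chart review, and power to detect an effect on timing alone will be low.
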